3. STUDY DESIGN

3.1 DESCRIPTION OF THE STUDY

Study YO39309 is a multicenter, open-label, Phase III clinical study with randomized and non-randomized arms designed to investigate the efficacy, safety, and pharmacokinetics of emicizumab in patients with hemophilia A regardless of FVIII inhibitor status.

Seventy patients aged ≥ 12 years who received episodic therapy with FVIII or bypassing agents prior to study entry and experienced at least 5 bleeds over the prior 24 weeks will be randomized in a 2:2:1 ratio (see [Figure 1](#)) to the following regimens:

- Arm A: Emicizumab prophylaxis at 3 mg/kg QW subcutaneously for 4 weeks, followed by 1.5 mg/kg QW subcutaneously
- Arm B: Emicizumab prophylaxis at 3 mg/kg QW subcutaneously for 4 weeks, followed by 6 mg/kg Q4W subcutaneously

- Arm C: No prophylaxis (control arm)

In addition, 15 pediatric patients with hemophilia A and inhibitors who received episodic therapy with bypassing agents prior to study entry will be enrolled to Arm D:

- Arm D: Emicizumab prophylaxis at 3 mg/kg QW subcutaneously for 4 weeks, followed by 1.5 mg/kg QW subcutaneously

The endpoints will be analyzed separately for the two randomized emicizumab arms (Arms A and B): 1.5 mg/kg QW and 6 mg/kg Q4W, as well as for the additional arm in pediatric patients (Arm D): 1.5 mg/kg QW.

Randomized patients will be stratified according to the number of bleeds the patient experienced over the 24 weeks prior to study entry—less than versus greater than or equal to 9—to ensure a balance of patients with lower versus higher number of bleeds in all arms.

To ensure a representative variety of patients with hemophilia A enrolled in this study to investigate the efficacy and safety profile of emicizumab in both inhibitor and non-inhibitor adolescent and adult populations, enrollment of up to 55 non-inhibitor patients will be permitted.

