Given the proven efficacy of prophylaxis, it can be expected that standard-of-care may evolve towards more widespread treatment of patients with prophylaxis regimens. However, for myriad reasons, currently only about half the patients in developed countries and less than 20% patients in China are managed with routine prophylaxis, making the episodic approach a commonly used standard care (Richards et al. 2007; Xue et al. 2011; Gringeri et al. 2012; Zappa et al. 2012; Jackson et al. 2014; Oldenburg and Brackmann 2014; Jackson et al. 2015; Oldenburg 2015). Thus, for the primary efficacy endpoint, patients with no prophylactic therapy will be compared with patients treated with prophylactic emicizumab. This study will only enroll patients who previously received episodic therapy; this approach will reduce heterogeneity in the study population, which is appropriate since the bleed rates for patients receiving therapy on an episodic versus prophylactic basis are significantly different (Valentino et al. 2012; Manco-Johnson et al. 2013; Powell et al. 2013; Antunes et al. 2014; Mahlangu et al. 2014; Windyga et al. 2014). To help balance measured and unmeasured covariates between the groups with prophylactic emicizumab and the control group with no prophylactic therapy, randomized patients will be stratified according to the number of bleeds they had over the 24 weeks prior to study entry (less than versus greater than or equal to 9 bleeds).

The primary efficacy analysis to assess the effect of emicizumab on bleed rate reduction will be performed at the earliest timepoint when all randomized patients have either completed 24 weeks of study treatment or discontinued from the study. Indeed, a similar follow-up period was used in recent studies that investigated the safety and efficacy of novel FVIII formulations and in the emicizumab global studies (Mahlangu et al. 2014; Kavakli et al. 2015; Konkle et al. 2015). Further, patients who experience frequent bleeds may not find it acceptable to be randomized to their usual episodic therapy for longer than 24 weeks prior to receiving emicizumab. For this reason, individual patients in the control arm will be offered the opportunity to switch to emicizumab after 24 weeks in the study.

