4.2 METHOD OF TREATMENT ASSIGNMENT AND BLINDING

This is an open-label study with randomized and non-randomized arms. Adolescents and adult patients who received episodic therapy with FVIII or bypassing agents prior to study entry will be randomized in a 2:2:1 ratio to receive either prophylactic emicizumab at 3 mg/kg QW subcutaneously for 4 weeks, followed by 1.5 mg/kg QW (Arm A) or 6 mg/kg Q4W (Arm B) subcutaneously, or to the control arm (no prophylaxis; Arm C). A central randomization procedure will be used for all patients who fulfill the entry criteria at screening. A block-based randomization method will be used, stratified by the number of bleeds in the last 24 weeks (<9 or \geq 9). The proposed randomization method is designed to balance treatment group assignment within the prognostic stratification factor.

This study will open one additional non-randomized arm (Arm D) to investigate the 1.5 mg/kg QW regimen in pediatric patients aged \leq 12 years with inhibitors. All patients will be recruited to Arm D.

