6.4.1 Primary Efficacy Endpoint

For the randomized arms (Arms A, B, and C), the primary efficacy objective is to evaluate the clinical effect of prophylactic emicizumab compared with no prophylaxis on the number of bleeds over time. The definition of a bleed for the primary analysis is

described in Section 4.5.8, with the primary endpoint comparing bleeds requiring treatment.

The primary efficacy analysis will be conducted after all randomized patients have completed 24 weeks in the study or the last randomized patient, yet to complete 24 weeks in the study, discontinues study participation, whichever occurs first, and using an intent-to-treat principle. The separate comparison of the number of bleeds over time between each of the randomized emicizumab arms and control arm will be performed using an NB regression model, which accounts for different follow-up times, with the patient's number of bleeds as a function of randomization and the time that each patient stays in the study included as an offset in the model. The model also includes the number of bleeds (<9 or ≥ 9) in the last 24 weeks prior to study entry as a stratification factor in the randomization. This analytic model estimates the rate ratio, λ_t / λ_c , which quantifies the risk of bleeding associated with prophylactic emicizumab (λ_t) in comparison to no prophylaxis (λ_c). Statistical significance is controlled at the 2-sided, 0.05 alpha (α) level. Of note, hierarchical testing is used to account for multiple testing and the first test to be included in the hierarchy is the emicizumab 1.5 mg/kg QW maintenance dose versus control. The second test will be 6 mg/kg Q4W maintenance dose versus control (or 3 mg/kg Q2W versus control, depending on global Study BO39182 data readout). The description below covers both hypotheses to be tested:

H_0 (null hypothesis): Rate Ratio = 1 versus H_1 (alternative hypothesis): Rate Ratio $\neq 1$.

The treatment effect therein is based on a contrast statement in the model with use of the SAS GENMOD procedure. Statistical significance at the pre-specified alpha level will be based on a Wald testing procedure. Bleed rates for prophylactic emicizumab and no prophylaxis and the rate ratio will be presented and include 95% confidence intervals.

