## **2. STUDY DESIGN**

[figure not shown]
Study YO39309 is a randomized, multicenter, open-label, Phase III clinical study will enroll patients aged 12 years or older with hemophilia A regardless of FVIII inhibitor status. Approximately 70 patients who received episodic treatment with FVIII or bypassing agents prior to study entry and experience at least 5 bleeds over the prior 24 weeks will be randomized in a 2:2:1 ratio to the following regimens:

- Arm A: Emicizumab prophylaxis at 3 mg/kg QW subcutaneously for 4 weeks, followed by 1.5 mg/kg QW subcutaneously
- Arm B: Emicizumab prophylaxis at 3 mg/kg QW subcutaneously for 4 weeks, followed by 6 mg/kg Q4W subcutaneously
- Arm C: No prophylaxis (control arm)

Randomization will be stratified according to the number of bleeds patients experienced over the last 24 weeks prior to study entry, <9 versus  $\geq 9$  (or ABR 18), to ensure a balance of patients with lower versus higher number of bleeds in all arms. All patients will continue usual episodic treatment with FVIII or bypassing agents in case of a breakthrough bleeding event.

To ensure a representative variety of patients with hemophilia A enrolled in this study to investigate the efficacy and safety profile of emicizumab in both inhibitor and non-inhibitor populations, enrollment of up to 55 non-inhibitor patients will be permitted. Study patients will be enrolled globally from China and other Asia Pacific countries. At least 60 patients will be enrolled from China and Hong Kong. The study schema is shown [Figure 1](#).

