## **3. STUDY CONDUCT**

### **3.1 RANDOMIZATION ISSUES**

Patients who received episodic treatment with FVIII or bypassing agents prior to study entry will be randomized in a 2:2:1 ratio to receive either emicizumab prophylaxis at 3 mg/kg/wk subcutaneously for 4 weeks, followed by 1.5 mg/kg/wk (Arm A) or 6 mg/kg/4wks (Arm B) subcutaneously, or to the control arm (no prophylaxis; Arm C). A central randomization procedure will be used for all patients who fulfill the entry criteria at screening. A block based randomization method will be used, stratified by the number of bleeds in the last 24 weeks (<9 or  $\geq$ 9). The proposed randomization method is designed to balance treatment group assignment within the prognostic stratification factor.

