### 4.5.1 Primary Efficacy Endpoint

The primary efficacy objective is to evaluate the clinical effect of prophylactic emicizumab compared with no prophylaxis on the number of bleeds over time. The definition of a bleed is described in Section 2.3.1. The primary endpoint is based on treated bleeds.

The comparison of the number of bleeds over time between the randomized treatment arms will be performed using an NB regression model, which accounts for different follow-up times, with the patient's number of bleeds as a function of randomization and the time that each patient stays in the study (the length of the efficacy period) included as an offset in the model. The model also includes the number of bleeds ( $<9$  or  $\geq 9$  according to the eCRF data) in the last 24 weeks prior to study entry as a stratification factor. This analytic model estimates the rate ratio,  $\lambda_t/\lambda_c$ , which quantifies the risk of bleeding associated with prophylactic emicizumab ( $\lambda_t$ ) in comparison to no prophylaxis ( $\lambda_c$ ). Statistical significance is controlled at the 2-sided, 0.05 alpha ( $\alpha$ ) level.

Of note, hierarchical testing is used to account for multiple testing and the first test to be included in the hierarchy is the emicizumab 1.5 mg/kg/wk maintenance dose versus control. The second test will be 6 mg/kg/4wks maintenance dose versus control. A global approach using a model statement (within GENMOD) with a 3-level categorical effect for treatment ("1.5 mg/kg/wk," "6 mg/kg/4wks," or "no prophylaxis") and an appropriate contrast statement will allow both tests to be performed via the following hypothesis

$H_0$  (null hypothesis): Rate Ratio = 1 versus  $H_1$  (alternative hypothesis): Rate Ratio  $\neq 1$ .

Statistical significance at the prespecified  $\alpha$  level will be based on a Wald testing procedure. Bleed rates for prophylactic emicizumab and no prophylaxis and the rate ratio will be presented and include 95% CIs.

The number of bleeds can also be annualized for each patient using the following formula:

$$ABR = (\text{Number of bleeds} / \text{Total number of days during the efficacy period}) \times 365.25.$$

Both the model-based method (estimated ABR from the NB model) and the method using the above formula (calculated ABR) will be used to describe the study results.

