#### **4.5.5 Subgroup Analyses**

Comparative subgroup analyses describing the primary endpoint, treated bleed rate, will be conducted for the randomized portion of the study. In addition, estimated ABR including 95% CI will be calculated for all treatment arms in each subgroup. Note, due to the small sample size, all subgroup analyses will be highly sensitive to variability caused by individual patients and need to be interpreted with caution. No p-values will be calculated.

The pre-specified subgroups are:

- Age: 12- $<18$ ,  $\geq 18$
- Age:  $<65$ ,  $\geq 65$
- Number of bleeds during 24 weeks prior to study entry:  $\leq 9$ ,  $> 9$
- Number of target joints: no target joint, any target joint

Subgroup analyses are subject to having sufficient patients in a subgroup to provide meaningful results.

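### The SAP 4.5.5 prior-bleed subgroup is cut at ≤9 versus >9, while randomization and the primary model cut at <9 versus ≥9, so patients with exactly 9 bleeds change group without explanation

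*SAP*

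**What the plan says.** **Subgroup definition.** SAP 4.5.5 lists the pre-specified subgroups for the treated bleed rate. The one on bleeding history reads "Number of bleeds during 24 weeks prior to study entry: $\leq 9$ , $> 9". The section plans comparative results and estimated ABRs with 95% confidence intervals for each arm in each subgroup. It plans no p-values, warns that individual patients can move the results, and makes each subgroup conditional on having enough patients.

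**Randomization.** Protocol 3.1 stratifies on the same 24-week count, "less than versus greater than or equal to 9", and Protocol 3.3 repeats it as "less than versus greater than or equal to 9 bleeds". Protocol 4.2 and SAP 3.1 use the same <9 or ≥9 split for the blocks. SAP 2 agrees: "Randomization will be stratified according to the number of bleeds patients experienced over the last 24 weeks prior to study entry, <9 versus" ≥9.

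**Primary model.** Protocol 6.4.1 enters the <9 or ≥9 count "in the last 24 weeks prior to study entry as a stratification factor in the randomization". SAP 4.5.1 uses the same split and takes the count "according to the eCRF data".

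Neither SAP 4.5.5 nor the SAP amendment rationale explains the different subgroup cut.

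**The concern.** Protocol 3.1 describes the strata as separating patients with lower and higher numbers of bleeds. A reader of the subgroup table will take its two rows to be those same groups, and they are not. The ≤9 row combines the whole <9 stratum with the patients from the ≥9 stratum who had exactly 9 bleeds. The >9 row is the ≥9 stratum without them.

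Two things follow. First, the table matches neither the randomization strata nor the covariate of the primary model. The balance that stratification is meant to provide therefore does not carry over fully to either row. Second, there are only 14 planned controls to divide between the two rows, so moving one of them can visibly change a subgroup rate. What is at stake is how clearly a descriptive table can be read, not the trial's conclusion.

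**Working it through.** **Step 1. Compare the two rules value by value.** Entry requires at least 5 bleeds (Protocol 4.1.1.1), so the eligible counts are 5, 6, 7 and upward.

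| Prior bleeds in 24 weeks | Randomization and primary model | SAP 4.5.5 subgroup | Same side? |
|---|---|---|---|
| 5 to 8 | <9, lower | ≤9, lower | yes |
| 9 | ≥9, higher | ≤9, lower | **no** |
| 10 or more | ≥9, higher | >9, higher | yes |

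Nine is the only discordant value. This step needs no assumption and establishes the inconsistency.

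**Step 2. How many patients might have exactly 9?** The plan has no figure to reproduce here, because it gives no distribution of prior counts. What follows is an illustration under stated assumptions.

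- Let Y be the prior count, negative binomial with mean m and variance m + k·m², observed only when Y ≥ 5.
- Range of k: Protocol 6.1 plans a control ABR of 18 with variance 10 × mean, which is 180. Solving 180 = 18 + k × 18² gives k = 162/324 = 0.5. The range used is half to double that, 0.25 to 1. Applying an on-study planning value to pre-study counts is an assumption.
- Range of m: 7 to 18 bleeds per 24 weeks before truncation. This range is also assumed.

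The quantity needed is p = P(Y = 9) / P(Y ≥ 5). Over the grid:

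- Smallest, at m = 18 and k = 0.25: p = 0.0395/0.9589 = 0.0412.
- Largest, at m = 7 and k = 0.25: p = 0.0658/0.6767 = 0.0973.

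**Step 3. Convert to patients.** Protocol 6.1 plans 70 patients, 14 of them controls.

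| Quantity | Formula | Low | High |
|---|---|---|---|
| Expected among all randomized | 70p | 2.9 | 6.8 |
| Expected among controls | 14p | 0.6 | 1.4 |
| Chance of at least one control | 1 − (1 − p)^14 | 45% | 76% |
| Chance of at least one of 70 | 1 − (1 − p)^70 | 95% | over 99% |

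**Step 4. Sensitivity outside the grid.**

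- m = 9, k = 0.05: p = 12.0%, or 8.4 of 70.
- Poisson with mean 9: p = 13.9%, or 9.8 of 70.
- m = 25, k = 0.25: p = 2.1%, or 1.5 of 70, with a 26% chance of at least one control.

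The affected group is small in all of these, but usually not empty.

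**Step 5. Reach of the effect.** The primary Wald tests, the testing hierarchy and the sample-size calculation do not use the ≤9 versus >9 cut. Alpha and power are therefore unchanged.

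**The case against.** The strongest reply is that this has no inferential consequence. The subgroup results are descriptive, carry no p-values, come with a warning in the SAP, and are run only if numbers allow. A subgroup boundary need not equal a stratification boundary: ≤9 versus >9 is defined at baseline and pre-specified, and it gives a legitimate descriptive comparison. That is correct, and it is why the point is minor.

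The loss of balance should also not be overstated. Block randomization limits imbalance within strata but does not guarantee exact balance, particularly with incomplete blocks. The <9 stratum stays whole inside the ≤9 row, so only the patients with exactly 9 dilute the balance. Prior bleeds are summarized by arm under SAP 4.4, so an imbalance would be visible.

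The patient counts rest on chosen distributions, and step 4 shows that they move when those choices change. That limits the illustration but not the finding, which depends only on comparing two inequalities.

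A misread inequality sign in the PDF conversion is unlikely. Both signs in SAP 4.5.5 would have had to change together, and as printed they form a coherent and exhaustive pair.

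None of this supplies a reason for the different cut.

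**Conclusion.** The inconsistency is real, and SAP 4.5.5 is the only place that uses the other cut. Its effect is confined to descriptive subgroup rate ratios and estimated ABRs, and those change only if a patient has exactly 9 prior bleeds. The documents do not say how many do. The illustration puts it at roughly 3 to 7 of 70, conditional on the truncated negative binomial assumptions above, and wider assumptions give about 1.5 to 10. This is a consistency correction worth making, not a source of bias in the primary result.

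**What to change.** In SAP 4.5.5, define the subgroup as <9 versus ≥9 bleeds in the 24 weeks before study entry, derived from the same eCRF variable as the covariate in SAP 4.5.1. If ≤9 versus >9 is intended, give the reason in that section. If results have already been seen, disclose that the change was made after that point.

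SAP 4.5.5 does not say how the subgroup model is fitted. If it is fitted separately within each of the two corrected subgroups, the stratum term becomes constant and drops out; a short note to that effect would help.

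The cost is one line of text, with no new data and no effect on the primary analysis. One limitation remains: groups built from eCRF counts will match the primary model covariate but could differ from the stratum entered at randomization for a patient whose count was recorded differently.

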## **4.6 PHARMACOKINETIC ANALYSES**

For all patients, pre-dose (trough) plasma concentrations of emicizumab will be presented descriptively by treatment arm, including arithmetic and geometric means, median, range, standard deviations, and coefficients of variation.

Nonlinear mixed effects modeling will be used to analyze the dose-concentration-time data of emicizumab following SC administration. Population PK parameters, such as clearance and volume of distribution, will be estimated, and the influence of various covariates, such as age, and body weight, on these parameters will be investigated graphically. Secondary PK parameters, such as area under the concentration-time curve (AUC), will be derived from individual post-hoc predictions. Data may be pooled with data from other studies. These analyses will be reported in a dedicated report.

## **4.7 SAFETY ANALYSES**

Safety will be assessed through descriptive summaries of adverse events, laboratory test results (serum chemistry and hematology, including complete blood count with differential), ECGs, vital signs, and antibodies to emicizumab and FVIII.

### **4.7.1 Exposure to Study Medication**

Information on study drug administration will be summarized by duration and cumulative dose. In addition, treatment exposure will be summarized, including delays and interruptions. The number of patients whose dose was up-titrated will be summarized.

Patient withdrawals from study treatment will be reported in patient listings and summary tables.

### **4.7.2 Adverse Events**

Adverse events will be summarized and presented by System Organ Class mapped term, appropriate thesaurus level, and toxicity grade (WHO Criteria) for each treatment arm. All adverse events will be coded using the current version of MedDRA at time of database closure. The total number and percentage of patients with at least one adverse event and total number of adverse events will be summarized. Separate adverse event summaries for serious adverse events, adverse events of special interest, severity, relatedness, and discontinuation/modification will be provided.

